7.5. Criteria for early termination of the trial

The trial may be completed prematurely:

- if the trial reveals serious adverse events associated with the use of the trial drug and makes its further use unacceptable from an ethical point of view;
- when new information is received that indicates a high risk for the trial participants;
- in the case of circumstances considered as force majeure events;
- at the request of the Federal Regulatory Authorities and at the decision of the Sponsor.

7.6. Exclusion of Research center

The trial conducted at a separate clinical center may be terminated if the Sponsor, Investigator, Regulatory Authorities, or the Ethics Committee of the clinical center deem it necessary for any reason.

8. DESIGN AND PLAN OF RESEARCH ACTIVITIES

The current trial is a multicenter, open-label, randomized, parallel-group, phase III b non-inferiority trial to compare the efficacy and safety of the trial drug.

The trial will include 336 patients with ischemic stroke. The patients will be monitored for 90 days: 1-2 days in the Neurological Intensive Care Unit and the Department of Neurology in the remaining days before discharge (on average 14 days), with an outpatient visit on the 90th day.

Start of research, initiation of centers: «_____» 20___

Enrollment of patients: «_____» 20___

Result processing and reporting: «_____» 20___

The enrollment period may be extended to total patient enrollment if a research center fails to enroll the planned number of patients. The end date of the trial is considered to be the end date of the trial in all patients involved.

In each research center, the subject of the trial is assigned a serial number that corresponds to the sequence of patient inclusion in the trial. The serial number is reflected in the Case Report Form (CRF). The list of patient's identification is stored in the trial file. Patients are included in the trial only after signing the Informed Consent Form.

Before the trial, all patients will undergo the following procedures: collection of thorough medical history, measurement of vital signs, physical examination, assessment of neurological status, CT/MRI scans of the brain, duplex scanning, and angiography of the brain vessels (if necessary), ECG, blood and urine samples for laboratory tests:

***complete blood count:** hemoglobin, red blood cells, hematocrit, leukocyte formula: neutrophils, eosinophils, basophils, monocytes, lymphocytes, platelets, ESR;

***biochemical blood parameters:** total protein, creatinine, urea, AST, ALT, CK, total bilirubin, glucose, sodium, potassium, cholesterol, HDL-C, triglycerides;

***coagulogram:** fibrinogen, activated partial thromboplastin time (aPTT), INR, prothrombin;

***common urine analysis:** color, transparency, reaction, density, glucose, protein, bilirubin/urobilinogen, white blood cells, red blood cells.

After enrollment, patients will be randomized using the "envelope method" into two equal groups of 168 patients each (a total of 336 people, including 10% who may have dropped out) and assigned to receive either Fortelyzin® or Actilyse®. Fortelyzin® will be given as single i.v. bolus over 5 - 10 seconds. Actilyse® will be administered following the instruction for use.

To compare the efficacy and safety of Fortelyzin® vs Actilyse®, patients will be monitored for 90 days after administration of the drug. During this period, patients will have 6 visits (Table 5).

Table 5. Plan of the trial

	V 1	V 2	V 3	V 4	V 5	V 6
	0	1 day	2 days	7 days	14 days	90 days
Signing Informed consent	+	–	–	–	–	–
Demographic data	+	–	–	–	–	–
Previous treatment	+	–	–	–	–	–
CT/MRI SCAN	+	+	–	+	–	–
ASPECTS	+	+	–	+	–	–
Dynamics of neurological status	–	+	+	–	–	–
Changes by organs and systems	–	+	+	+	+	–
TOAST criteria	–	–	+	–	–	–
Medical history	+	–	–	–	–	–
Measurement of vital signs	+	+	+	+	+	+
Physical examination	+	–	–	–	–	–
Concomitant diseases	+	–	–	–	–	+
NIHSS	+	+	+	+	+	+
Bartel	–	–	–	+	+	+
Rankin	+	–	+	+	+	+
Meningeal symptoms	+	+	+	+	+	–
ECG	+	–	–	+	+	–
Duplex scanning of the major arteries of the head (if necessary)	+	–	–	+	–	–
Coagulogram	+	+	+	+	+	–
Complete blood count	+	–	+	+	+	–
Biochemical blood analysis	+	–	–	+	+	–
Blood sampling for Pharmacokinetic analysis	–	+	–	–	–	–
Common urine analysis	+	–	+	+	+	–
Inclusion/Exclusion criteria	+	–	–	–	–	–
Angiography of cerebral vessels (if necessary)	+	–	–	–	–	–
Administration of Fortelyzin® or Actilyse®	–	+	–	–	–	–
Change in concomitant therapy	–	+	+	+	+	+
Registration of AE	–	+	+	+	+	+
Bleeding assessment	–	+	+	+	+	–

9. TRIAL PROCEDURES

Visit 1 (Start of the trial)

Prior to administration of the trial drug, all patients will undergo the following procedures:

- determination of inclusion/non-inclusion criteria
- signing of Informed consent
- collection of demographic data (date of birth, sex)
- collection of medical history (duration of the underlying disease, previous therapy, allergological anamnesis, etc.)
- physical examination
- evaluation of changes by organs and systems
- assessment of neurological status using the NIHSS and modified Rankin scales (mRS)
- Duplex scanning of the major arteries of the head (if necessary)
- CT/MRI examination of the brain
- assessment of CT changes according to ASPECTS (Alberta Stroke Program Early CT Score)
- angiography of the cerebral vessels (if necessary)
- blood sampling for hematological and biochemical analyses
- coagulogram
- common urine analysis
- ECG
- assessment of the patient's compliance with the inclusion/exclusion criteria
- randomization

Assignment of individual patient identification code (IPIC)

The Investigator must ensure the anonymity of the trial subjects. The full names of all patients participated in the trial are strictly confidential.

After signing the Informed Consent Form, each patient will be assigned an Individual Patient Identification Code (IPIC) in accordance with the current legislation (Table 6).

Table 6. Individual Patient Identification Code

Permission of the Ministry of Health of the Russian Federation No.	Permission's date of issue, DD/MM/YYYY/	Serial number of the medical organization specified in the Permission	Patient's initials	Patient's date of birth, DD/MM/YYYY/	A unique number assigned to the patient by the Investigator, consisting of letters and numbers (the name of the protocol and the screening number under which the patient was included in the trial)
--	---	---	--------------------	--------------------------------------	--

The individual patient identification code (IPIC) is established by the Insurant based on the patient data provided by the Investigator. The individual patient identification code is reported by the Insurant to the Investigator for inclusion in his medical documentation. The IPIC will be reflected in the primary documentation, Case Report Form, and Patient Information Sheet with the informed consent form. The IPIC will be transmitted by the Code Registry by the Insurant to the Insurer.

The individual identification code assigned to the patient is not subject to change.

The Investigator should maintain a separate Identification Registry containing the individual numbers, surnames, dates of birth, addresses, phone numbers, and medical records (if available). Only the initials, dates of birth, and unique patient numbers that are part of the Individual Patient Identification Code will be used in the report and trial documentation.

The randomization plan will be known by the Principal Investigator and Regulatory Authorities.

Visit 2.

- Administration of Fortelyzin® or Actilyse®.
- On Visit 2, the changes in neurological status will be recorded, as well as registration and evaluation of bleeding and adverse events based on patient complaints, data from neurological, physical, and laboratory-instrumental studies.

Table 7. Monitoring of parameters at the moment of thrombolysis

Trial parameter	Frequency of examination
BP	Every 15 minutes to 2 hours after the start of thrombolysis
Vital signs	Every 30 minutes for 6 hours
NIHSS	Every 15 minutes for 1 hour
Meningeal symptoms	Every 15 minutes for 1 hour

Table 8. Monitoring of parameters during the first day (24h) after thrombolysis

Trial parameter	Frequency of examination
BP	Every hour until the end of the day (within 24 hours)
Vital signs	Every 30 minutes to 6 hours, then every hour until the end of the day
Meningeal symptoms	Every hour for 24 hours
NIHSS	Every hour for 24 hours

- CT/MRI 24 hours after TLT or if the patient's condition worsens
- assessment of CT changes according to ASPECTS
- registration of adverse events (AE)
- assessment of bleeding

All adverse events identified should be recorded in the Case Report Form (CRF). The Investigator should report the adverse events to Roszdravnadzor within the next 24 hours. The assessment of bleeding is carried out according to the corresponding scales (see Safety assessment). Monitoring of coagulogram parameters (fibrinogen) will be carried out within 24 h from the time of Fortelyzin® or Actilyse®

administration. CT/MRI examination of the brain will be repeated 24 hours after the thrombolysis or if the patient's condition worsens.

During the visit, patients will receive treatment in accordance with the Russian Clinical Guidelines for Thrombolytic Therapy in Ischemic Stroke, 2015.

Visit 3.

- verification of the stroke subtype according to TOAST criteria
- measurement of vital signs
- physical examination
- assessment of neurological status scales scores
- coagulogram
- complete blood count
- common urine analysis

Visit 4.

- measurement of vital signs
- physical examination
- assessment of neurological status scales scores
- CT/MRI scans
- assessment of CT changes according to ASPECTS
- ECG
- ultrasound examination of brain vessels (if necessary)
- coagulogram
- complete blood count
- biochemical analysis of blood
- common urine analysis.

Visit 5.

- measurement of vital signs
- physical examination
- assessment of neurological status scales scores

- ECG
- coagulogram
- complete blood count
- biochemical analysis of blood
- common urine analysis.

During visits 2-5, information about adverse events and bleeding will be collected and recorded into the Case Report Form. The data on adverse events will be shared with the Sponsor. In addition, information about changes in concomitant therapy will also be recorded.

Visit 6.

- measurement of vital signs
- collection of information about SAE and AE, as well as recording the Bartel index scores, Rankin and NIHSS scale scores
- collection of information about concomitant diseases.

Unscheduled visits

Unscheduled visits may be made at the discretion of the Investigator or at the initiative of the patient. For all unscheduled visits, the corresponding CRF page should be filled out.

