HR	– heart rate
EC	– Ethics Committee
ECG	– electrocardiography
BI	– Barthel Index for activities of daily living
ECASS	– European Cooperative Acute Stroke Study
Hb	– hemoglobin
Ht	– hematocrit
ICH	– International Conference on Harmonisation
GCP	– Good Clinical Practice
GUSTO	– Global Use of Strategies to Open Occluded Coronary Arteries
Na ⁺	– Sodium in blood
NIHSS	– National Institutes of Health Stroke Scale
NYHA	– New York Heart Association
TIMI	– Thrombolysis in Myocardial Infarction
TFC	– TIMI Frame Count
TOAST	– Trial of ORG 10172 in Acute Stroke Treatment

PROTOCOL SUMMARY

Official Title:	Multicenter open-label randomized comparative trial of the efficacy and safety of single-bolus intravenous injection of Fortelyzin® (manufactured by Supergene, LLC) and bolus infusion of Actilyse® (manufactured by Boehringer Ingelheim Pharma GmbH) in patients with ischemic stroke
Short title:	FRIDA
Trial phase:	III b
Trial aim:	Assessment of the efficacy and safety of single-bolus intravenous injection of Fortelyzin® in comparison with bolus infusion of Actilyse® in patients with ischemic stroke
Trial objectives:	
 • To assess the efficacy of single-bolus intravenous injection of Fortelyzin® in comparison with bolus infusion of Actilyse® in patients with ischemic stroke • To assess the safety and possible adverse events of single-bolus intravenous injection of Fortelyzin® in comparison with bolus-infusion of Actilyse® in patients with ischemic stroke
Trial design:	A multicenter, open-label, randomized, comparative, parallel-group non-inferiority trial of efficacy and safety. In clinical centers, patients will be randomized using the "envelope method" into two equal groups of 168 patients each (a total of 336 people, including 10 % of those who may have dropped out) and assigned to receive either Fortelyzin® or Actilyse®. The drugs will be administered no later than 4,5 hours after ischemic stroke onset and after signing the informed consent. Fortelyzin® will be given as single i.v. bolus over

	
5-10 seconds. Actilyse® will be administered in accordance with the instruction for use.
 
Patients will be monitored for 90 days: 1-2 days in the Neurological Intensive Care Unit and the Department of Neurology in the remaining days before discharge (on average 14 days), with an outpatient visit on the 90th day.
 
Enrollment of patients into the trial will be conducted on a competitive basis.

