Safety criteria:	
 Safety endpoint - overall mortality on day 90. Safety endpoint - hemorrhagic transformation (all cases). Safety endpoint - symptomatic hemorrhagic transformation (as defined by ECASS III). The number of SAE and AE by organs and systems.

CLINICAL TRIAL PROTOCOL

Finally:	Each research center prepares a report, which is signed by the Principal Investigator and approved by the head of the medical institution, where the center is based. The submission deadline is up to 1 month after the completion of the trial. The statistical processing is carried out by an independent statistical expert according to the Case Report Form (CRF).
-----------------	---

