4.2. Patient Information Sheet

Informed consent will be obtained from all prospective study participants before any research procedures are initiated. Prior to this, the Investigator must fully inform a patient about all aspects of clinical research, including its purposes, study procedures, expected risks and benefits of participation, and voluntariness of participation.

The patient must be provided with written information about the study (Information Sheet), approved by the Ethics Committee. The patient's information sheet will contain all information about the planned clinical trial, as well as the terms of confidentiality and the use of the patient's data. The rights, safety, and well-being of the participants will take priority and prevail over the interests of science and society. If necessary, information about the procedure for obtaining informed consent from patients/volunteers can be submitted to the Ethics Committee.

Prior to the patient's participation in the clinical trial, two (2) copies of the Informed Consent Form with the patient's name must be signed and personally dated by the patient or the patient's legal representative, or by a person who conducted the informed consent discussion. One copy of signed and dated written Informed Consent will be provided to the patient, and the other will be kept by the Investigator.

When the patient's condition does not allow him/her to express his/her will and there is no legal representative and the need for treatment is urgent, the question of medical intervention in the interest of the patient and his/her inclusion in the study is resolved by a council of physicians, and if it is not possible – by his/her attending (duty) physician with following notification of the Principal Investigator, officials of the medical institution and the legal representative.

The Patient Information Sheet and Informed Consent Form must be reviewed and approved by the Ethics Committee. The final version of the Study Protocol, Individual Patient Registration Form, information for the patient, and Informed Consent Form must be approved by the Russian Ministry of Health and the Local Ethics Committee (if any) at the Research Center.

All subsequent amendments to the above-mentioned documents will also be submitted for approval to these institutions. In addition, these same institutions will be informed about all adverse events associated or possibly related to the use of the study drug.

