7.2. Exclusion criteria

- The time of the onset of the first symptoms is more than 4.5 hours from the onset of the disease or the time of the onset of the first symptoms of a stroke is not known (for example, the development of a stroke during sleep - the so-called "night stroke").

- Increased sensitivity to alteplase, gentamicin (residual traces from the production process).
- Systolic blood pressure greater than 185 mm Hg or diastolic blood pressure greater than 110 mm Hg or the need for intravenous administration of drugs to reduce the blood pressure to these boundaries.
- Neuroimaging (CT, MRI) signs of intracranial hemorrhage, brain tumors, arteriovenous malformation, brain abscess, aneurysm of cerebral vessels.
- Surgery on the brain or spinal cord.
- Suspicion of subarachnoid hemorrhage.
- Signs of severe stroke: clinical signs (stroke scale NIH > 25), neuroimaging (according to CT of the brain and/or MRI of the brain in the DWI, the ischemia focuses on the territory of more than 1/3 of the MA pool).
- Simultaneous administration of oral anticoagulants, for example, warfarin with INR > 1.3.
- The use of direct anticoagulants (heparin, heparinoids) in the 48 hours preceding the stroke with APTT values above the norm.
- Prior stroke or severe head injury within 3 months.
- Significant regression of neurological symptoms during the observation of the patient
- Light neurological symptoms (NIH < 4 points)
- Hemorrhagic stroke or stroke, unspecified in history.
- Strokes of any genesis in the history of a patient with diabetes mellitus.
- Gastrointestinal bleeding or bleeding from the genitourinary system in the last 3 weeks. Confirmed exacerbations of gastric ulcer and duodenal ulcer during the last 3 months.
- Extensive bleeding, present or within the previous 6 months.

- Severe liver disease, including liver failure, cirrhosis, portal hypertension (with varicose veins of the esophagus), active hepatitis.
- Acute pancreatitis.
- Bacterial endocarditis, pericarditis.
- Aneurysms of arteries, malformations of arteries and veins. Suspicion of exfoliating aortic aneurysm.
- Neoplasms with an increased risk of bleeding.
- Large operations or severe injuries within the last 14 days, minor surgery or invasive manipulation in the last 10 days.
- Puncture of uncompensated arteries and veins during the last 7 days.
- Prolonged or traumatic cardiopulmonary resuscitation (more than 2 min).
- Pregnancy, obstetrics, 10 days after delivery.

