20. REPORTING

Each research center compiles a report, which is signed by the Principal Investigator and approved by the head of the medical institution on the basis of which the center is located.

The statistical processing is carried out by an independent statistical expert on the basis of the CRF.

The deadline for report submission is up to 1 month after the completion of the trial.

The final report will contain clinical and statistical reports, as well as appendixes with individual data and statistical analysis.

The suggested structure of the report: the purpose of the trial, methods (including any deviations from the Trial Protocol), evaluation of the results, discussion of adverse events, and their interpretation.

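### The Principal Investigator may know the randomisation plan, with no time limit and no envelope safeguards, so allocation concealment is not assured in this open-label trial

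*Combined protocol and SAP*

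**What the plan says.** Section 9, at the end of the Visit 1 text, states: "The randomization plan will be known by the Principal Investigator and Regulatory Authorities". No date, condition or exception is attached.

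The allocation method is named twice and described nowhere. The Protocol Summary (Trial design) says "In clinical centers, patients will be randomized using the" envelope method. Section 8 says "After enrollment, patients will be randomized using the" same method, without repeating where this happens. Section 9 lists randomisation as the last Visit 1 step, after consent, baseline NIHSS and the eligibility check. Section 8 also says that in each centre "the subject of the trial is assigned a serial number that corresponds to the sequence of patient inclusion in the trial", and that the trial is open-label.

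Three places bear on who the Principal Investigator is:

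- Protocol Summary (Finally): "Each research center prepares a report, which is signed by the Principal Investigator and approved by the head of the medical institution".
- Section 20: "Each research center compiles a report, which is signed by the Principal Investigator".
- Section 4.2, on patients who cannot consent and have no representative: a council of physicians or, failing that, the duty doctor decides on inclusion, the latter being the "physician with following notification of the Principal Investigator, officials of the medical institution and the legal representative".

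**The concern.** Concealment means that whoever decides whether to enter a patient cannot know which treatment comes next. The section 9 sentence grants knowledge of the plan to a role that elsewhere sits at the centres, and nothing else in the protocol restores the protection. Placing randomisation after the eligibility check prevents reconsideration once an envelope has been opened. It does not stop someone who already knows the next assignment from judging this patient eligible or not.

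There is room for such judgement. One exclusion in section 7.2 is "Significant regression of neurological symptoms during the observation of the patient", which depends on the observer. Steering on a recorded factor such as baseline NIHSS would show in the data and could be adjusted for. Steering on an unrecorded impression of prognosis could not. The bias could favour either drug.

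**Working it through.** **Reading the passages together**

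1. *What is the plan?* If it meant only the method, there would be little reason to say who may know it, because the envelope method is printed in the protocol itself. The sentence makes most sense if it refers to the allocation list.
2. *Who is the Principal Investigator?* The Summary and section 20 have one signing the report of each centre. Section 4.2 places the role beside the institution's officials. A centre-level role is the more natural reading, although a single coordinating investigator is possible.
3. *Is there a compensating safeguard?* No section says who generates the sequence, who holds the list or envelopes, whether envelopes are sealed, opaque or numbered, or whether opening is logged. No central allocation is described and no separate manual is cited. Section 18 refers to stratification variables but none is defined. Section 19 does not name envelopes or allocation among the items to be checked.
4. *Does the emergency pathway help?* In part. Where a council or duty doctor decides and the Principal Investigator is told afterwards, that person's foreknowledge would not act. This covers only patients who cannot express their will and have no legal representative.

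**How small a shift would matter (illustration, not an estimate of bias)**

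Inputs from section 17: 54.8% responders in both arms, margin 16 points, two-sided 5%, power 80%, 152 per arm, 168 per arm with dropout. Assumption: a Wald two-sided 95% interval, because section 18 names no non-inferiority interval.

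The plan's own figure first:

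n = (1.960 + 0.842)² × 2 × 0.548 × 0.452 / 0.16² = 151.9, so 152 per arm. This matches. With 10% added, 152 × 1.10 = 167.2, so 168.

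Then:

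- SE = √(2 × 0.548 × 0.452 / n)
- Observed difference needed to pass = -16 + 1.96 × SE
- If the true difference is -16 and selection shifts it by b points in favour of the study drug, P(pass) = 1 - Φ(1.96 - b/SE)
- Shift that doubles 2.5% to 5%: b = (1.960 - 1.645) × SE

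| | 152 per arm | 168 per arm |
|---|---|---|
| SE (points) | 5.71 | 5.43 |
| Passing threshold (points) | -4.81 | -5.36 |
| P(pass), b = 0 | 2.5% | 2.5% |
| b giving 5% (points) | 1.80 | 1.71 |
| the same in responders, one arm | 2.7 | 2.9 |
| P(pass), b = 3 | 7.6% (4.6 responders) | 8.0% (5.0 responders) |
| P(pass), b = 5 | 13.9% (7.6 responders) | 14.9% (8.4 responders) |

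Taking the SE at the boundary instead (54.8% against 38.8%: 5.65 and 5.37 points) changes little: 1.78 and 1.69 points for doubling, 7.7% to 8.1% at b = 3, and 14.1% to 15.2% at b = 5.

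**The case against.** The strongest reply is that the sentence is ambiguous in two ways. The plan may mean the scheme rather than the list. The Principal Investigator may be one coordinating person: section 9 usually calls the bedside role the Investigator, and section 4 uses the title Principal Investigator for the lead of a national guideline. The sentence can also be read as a restriction, meaning these two parties and nobody else. Further, the serial number in section 8 is not tied to envelope order, most eligibility criteria are measured rather than judged, and the shift calculation would be the same for any source of bias.

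Some of this stands. The documents do not settle who is meant, the serial number does not by itself make the next assignment predictable, and the figures say nothing about how likely or how large a bias would be. They show only how sensitive the test is near its boundary, for a shift in one direction.

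The rest does not remove the point. The restrictive reading still leaves the Principal Investigator with the plan. If a single coordinator is meant, or only the scheme, the missing envelope and custody rules still leave concealment unsecured. One judgement-based criterion is enough to give discretion. Knowledge of treatment after allocation follows from the declared open-label design and is a separate matter; the issue here is knowledge before allocation.

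**Conclusion.** The concern holds. As written, the protocol gives the Principal Investigator the randomisation plan without a time limit and describes no safeguard that would keep the next assignment hidden at the centres. This is a stated rule that weakens protection against selection bias, and not merely a missing detail. It should be corrected before enrolment, since steering on unrecorded judgement cannot be repaired in the analysis.

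That conclusion rests on the text, not on an estimated bias. It assumes the ordinary meaning of the plan as the allocation list and the centre-level meaning of Principal Investigator. If either is wrong, the narrower finding, that concealment is not assured because custody and envelope handling are unspecified, still stands. Nothing here shows that selection bias occurred, and the planned sample size is unaffected.

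**What to change.** Replace the section 9 sentence with text such as:

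> The randomisation list is generated and held by a person independent of recruitment, enrolment and outcome assessment (for example the independent statistical expert) and is available to Regulatory Authorities. No investigator, including any Principal Investigator, has access to it before enrolment is complete.

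Add to section 8:

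> Envelopes are sequentially numbered, opaque and sealed, and are opened in order only after consent, eligibility and baseline NIHSS have been recorded in the CRF. The date and time of opening are logged.

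The Monitor can check the log at the visits already planned in section 19. An independent statistical expert is already named in the Summary and section 20. The cost is an amendment, which under sections 4.1 and 4.2 goes to the Ethics Committee and the other approving bodies, plus preparing, distributing and logging envelopes by someone outside recruitment. No patients, visits or clinical rules change, and the regulators keep their access.
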